9.0 MEASUREMENT OF EFFECT

9.1 *Antitumor Effect- Solid Tumors*

9.1.1 Definitions:

Evaluable for toxicity: All patients will be evaluable for toxicity immediately following brachytherapy.

Evaluable for disease control assessment: All patients with at least 2 follow-up PSAs will be evaluable for disease control. After brachytherapy, these patients will have their disease status classified according to the definitions stated below.

Biochemical (PSA) recurrence (BR): Based on RTOG Phoenix definition: an increase of the PSA level at least 2 ng/ml greater than the minimum level after therapy (REF: phoenix paper)

All patients with BR should undergo at least MP-MRI of the prostate and bone scan. Biopsy of any suspicious lesions within the prostate gland on MP-MRI is encouraged.

Freedom from Biochemical (PSA) Recurrence (FFBR):

The time to PSA failure will be measured from the date of treatment to the date of a rise by 2 ng/mL or more above the nadir PSA. The time of failure will be the date of the first PSA that is 2 ng/mL or more above the lowest prior post-treatment PSA value. If the rise in PSA to $>$ nadir + 2 occurs during the first 36 months followed by a subsequent non-hormonal induced PSA decrease, patients will **not** be considered PSA failures.

As a benign “spike” or “bounce” in the PSA value has been described in as many as 35% of patients 12-36 months following brachytherapy, intervention for a PSA failure should be based on a positive prostate biopsy at least 24 months post-treatment and/or clinical evidence of distant relapse (i.e., bone scan, CT scan, etc).

Local Failure (LF): This rating will be assigned when there is biopsy-proven disease progression or recurrence at the lesion within the prostate treated with protocol therapy. Histologic criterion for local failure is the presence of prostatic carcinoma upon biopsy more than 2 years after the start of treatment. Residual carcinoma on biopsy should show minimal radiation effect and should be in clinical scenario of increasing PSA.

Local Control (LC): Absence of local failure. This will be assumed in patients with a controlled PSA and for those with PSA failure but no radiographic, clinical, or biopsy-proven disease at the lesion treated with protocol therapy.

Freedom from Local Failure (FFLF): The time to local progression will be measured from the date of treatment to the date of local failure.

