Elsewhere Prostate Failure (EPF): This rating will be assigned when there is biopsy-proven disease progression/recurrence at outside the lesion treated with protocol therapy but within the prostate or seminal vesicles.

Elsewhere Prostate Control (EPC): Absence of EPF. Will be assumed in patients with a controlled PSA and in patients with PSA failure but no radiographic, clinical, or biopsy-proven disease at the site treated with protocol therapy.

Freedom from Elsewhere Prostate Failure (FFEPF): The time to elsewhere prostate failure will be measured from the date of treatment to the date of EPF.

Regional Failure (RF): Visible disease on imaging that occurs in lymph nodes within the usual regional spread pattern of prostate cancer

Regional Control (RC): Absence of regional/nodal recurrence.

Freedom from Regional Failure (FFRF): The time to regional failure will be measured from the date of treatment to the date of RF.

Distant Metastasis (DM): Visible disease on imaging that occurs elsewhere in the body including non-regional lymph nodes.

Freedom from Distant Metastasis (FFDM): The time to distant metastasis will be measured as the date of treatment to the date of DM.

Freedom from hormone therapy (FFHT): The time from the date of treatment to first administration of androgen deprivation therapy

Disease-free Survival (DFS): Defined as the duration of time from the date of completion of treatment to either BR, LF, EPF, RF, DM, or death.

Cause-specific Survival (CSS): Defined as the duration of time from the date of completion of treatment to death from prostate cancer.

Overall Survival (OS): Defined as the duration of time from the date of completion of treatment until death from any cause.

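### Disease-free survival (DFS) counts biochemical recurrence (BR), which has no bounce exception, while freedom from biochemical recurrence (FFBR) has one, so a reversing PSA rise can be a DFS event without being a PSA failure

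*Combined protocol and SAP*

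**What the plan says.** All the relevant definitions are in Section 9.1.1.

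- **BR** is "an increase of the PSA level at least 2 ng/ml greater than the minimum level after therapy". The entry has no time window, no confirmation and no provision for a rise that later reverses. It also makes BR the trigger for MRI and a bone scan.
- **FFBR** dates the failure as follows: "The time of failure will be the date of the first PSA that is 2 ng/mL or more above the lowest prior post-treatment PSA value". It then adds an exception. If a rise above nadir + 2 "occurs during the first 36 months followed by a subsequent non-hormonal induced PSA decrease", the man is not counted as a PSA failure. The reason given is that a benign bounce "has been described in as many as 35% of patients 12-36 months following brachytherapy".
- **DFS** is "Defined as the duration of time from the date of completion of treatment to either BR, LF, EPF, RF, DM, or death". Its PSA component is the defined term BR. It does not mention FFBR and has no bounce exception of its own.

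The two endpoints also start their clocks differently. FFBR runs from the date of treatment, DFS from the date treatment is completed.

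DFS is a listed secondary endpoint (Section 2.3.2.8). Section 12.2 plans only to describe it. Neither Section 12.2 nor Section 12.3 says which PSA rule DFS uses.

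**The concern.** The same PSA record can be classified in opposite ways by two endpoints of one trial, for no reason other than wording. The FFBR entry shows that the authors regard a reversing early rise as benign. DFS as written still counts it, and dates the event at the rise. Two analysts could each follow the protocol and report different DFS curves.

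The discrepancy runs in one direction. Every man affected is an event under BR and not under the FFBR rule, so DFS can only be lower under BR. The effect falls mainly in the 12 to 36 month window in which the protocol places bounces. Section 1.5 says the data are meant to support a phase III trial of disease control, so the DFS description should have a single meaning.

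**Working it through.** **1. The plan's own figures.** No figure is stated for DFS or FFBR. The only design figures are for toxicity in Section 12.2: continue with 0 or 1 toxicities in 7, and reject with 4 or fewer in 24. The rejection probability is the sum of Bin(a; 7, p) × Bin(b; 17, p) over a ≤ 1 and a + b ≤ 4. This gives 0.0462 at p = 0.33 and 0.809 at p = 0.10, which match the stated .046 and 81%. PSA does not enter this calculation.

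**2. The rules applied to one record.** Take a constructed series on the Section 8.3 schedule (months 3, 6 and 12, then every 6 months), with no hormones after protocol treatment:

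| Month | 3 | 6 | 12 | 18 | 24 | 30 | 36 |
|---|---|---|---|---|---|---|---|
| PSA (ng/mL) | 0.1 | 0.2 | 0.8 | 2.4 | 0.9 | 0.6 | 0.5 |

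- The nadir is 0.1, so the threshold is 0.1 + 2 = 2.1. The month 18 value is 2.4 − 0.1 = 2.3 above nadir.
- BR is met at month 18, so this is a DFS event at month 18.
- Under FFBR, the rise is within 36 months and PSA falls to 0.9 at month 24 without hormones. He is not a PSA failure.

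A sustained rise is an event under both rules. A PSA that never reaches nadir + 2 is an event under neither. The rules differ only for rises in the first 36 months that later reverse.

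**3. Number of men affected.**

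- N = 24 (Section 12.2), which assumes the trial goes on to its second stage.
- Bounce rate b = 0.35, the protocol's maximum (Section 9.1.1).
- Share s of bounces that reach nadir + 2: not in the documents, so assumed over a range.

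Expected number = 24 × b × s. Chance of at least one = 1 − (1 − b × s)^24.

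| Assumed s | b × s | Expected men of 24 | Chance of at least one |
|---|---|---|---|
| 5% | 0.0175 | 0.4 | 35% |
| 10% | 0.035 | 0.8 | 57% |
| 25% | 0.0875 | 2.1 | 89% |
| 50% | 0.175 | 4.2 | 99% |

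Every row uses the maximum bounce rate, so each is a ceiling for its value of s. At b = 0.15 and s = 10%, for example, the expected number is 24 × 0.15 × 0.10 = 0.36 men and the chance of at least one is 30%.

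**4. Effect on the DFS estimate.** With complete follow-up, one extra event moves DFS by 1/24 = 4.2 percentage points. As an illustration, assume that 36-month DFS is 60% under the FFBR rule and that bounces are independent of true failure. Under BR it would read 0.60 × (1 − b × s): about 59%, 58%, 55% and 50% for the four rows above.

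**The case against.** The strongest reply is that there is only one event. FFBR means freedom from BR, the two entries are adjacent, and the second can be read as supplying the date and the exception for the first. The exception is phrased as a status of the patient, and the local control and elsewhere-prostate control entries also use PSA failure as a general status. On that reading a bounce is not BR, and DFS is consistent with FFBR.

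This is plausible and may be what was meant, but no sentence says it. The BR entry also works against it. BR triggers imaging, whereas the exception needs a later PSA before it can be applied. That fits BR as an immediate flag and the FFBR rule as the final classification. DFS names the flag.

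Three further objections stand and limit the point:

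- The 35% is a maximum and covers bounces of unstated size. A reader might infer that 24 × 0.35 = 8.4 men would be wrongly scored. That would need every bounce to reach nadir + 2, which the documents do not say.
- Not every discordant event is certainly false. The exception accepts any later non-hormonal fall, with no minimum size or duration, so some reversing rises could be true recurrences.
- A reader might infer that the planned 24-month analysis is biased. Section 12.3 assigns that analysis to relapse-free survival. Section 12.2 lists relapse-free survival separately from DFS, and Section 9.1.1 does not define it. The documents do not support the link.

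**Conclusion.** The point holds as an unresolved inconsistency in a secondary endpoint. On the literal text, a man with a rise of at least 2 ng/mL above his post-therapy minimum that reverses without hormones within the exception's terms has a DFS event but is not a PSA failure in FFBR. This can lower descriptive DFS over roughly months 12 to 36.

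About 0.4 to 4.2 of 24 men are affected. This rests on the protocol's maximum bounce rate and on an assumed 5% to 50% of bounces reaching nadir + 2. The documents do not allow a narrower range.

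It would go too far to say that the authors intended bounces to count against DFS, or that the trial's main conclusion is at risk. DFS has no test, threshold or sample size attached to it. The primary toxicity test, N, type I error and power do not change.

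**What to change.** Define the biochemical failure event once in Section 9.1.1, for endpoint scoring only. The definition should state:

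- the event date;
- the bounce exception in its final form, including what counts as a decrease;
- how a rise with no later PSA is handled.

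Then have both FFBR and DFS cite that definition in place of their separate wording. Choose one time origin for the two endpoints, since date of treatment and date of completion now differ. Report DFS under raw nadir + 2 as a sensitivity analysis, so that the effect of the exception is visible. The use of BR as a work-up trigger can remain a separate matter.

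The cost is a short wording change, with no new patients, visits or data. It is best made before the outcome data are examined, so that the rule is not chosen in the light of the results. The one drawback is that a man with a recent rise has provisional DFS status until his next PSA, normally 6 months later on the long-term schedule in Section 8.3.

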10.0 ADVERSE EFFECTS

10.1 *Data Safety Monitoring Plan*

This trial will be conducted in accordance with the Data Safety Monitoring Plan (DSMP) of the Cardinal Bernardin Cancer Center of Loyola University Medical Center.

10.2 *Adverse Event Monitoring*

All patients experiencing an adverse event, regardless of its relationship to study therapy, will be monitored until:

- The adverse event resolves or the symptoms or signs that constitute the adverse event return to baseline;
- Any abnormal laboratory or imaging results have returned to baseline;

- There is a satisfactory explanation other than the study treatment for the changes observed; or
- Death.

10.3 ***Definitions***

10.3.1 Definition of Adverse Event

An adverse event (AE) is any untoward medical occurrence in a patient receiving study treatment, which does not necessarily have a causal relationship with this treatment. An AE can therefore be any unfavorable and unintended sign (including an abnormal laboratory finding), symptom, or disease temporally associated with the use of an experimental intervention, whether or not related to the intervention.

An adverse event will be determined to be radiation-related or non-radiation-related based on review by the treating physician and principle investigator.

10.3.2 Severity of Adverse Events

All non-hematologic adverse events will be graded according to the NCI CTCAE version 4.03. The link to CTCAE version 4.03 is available in Appendix A.

If no CTCAE grading is available, the severity of an AE is graded as follows:

Mild (grade 1): The event causes discomfort without disruption of normal daily activities

Moderate (grade 2): The event causes discomfort that affects normal daily activities or requires pharmacologic intervention to treat.

Severe (grade 3): The event makes the patient unable to perform normal daily activities or significantly affects his/her clinical status or requires an operative procedure to treat.

Life-threatening (grade 4): The patient was at risk of death at the time of the event.

Fatal (grade 5): The event caused death.

10.3.3 Serious Adverse Events (SAE)

A serious adverse event is defined in regulatory terminology as any untoward medical occurrence that:

10.3.3.1 *Results in death.*

If death results from (progression of) the disease, the disease should be reported as the event itself.

10.3.3.2 *Is life-threatening.*

If the patient is at risk of death at the time of the event; it does not refer to an event that hypothetically might have caused death if it were more severe.

10.3.3.3 *Requires in-patient hospitalization or prolongation of existing hospitalization for ≥ 24 hours.*

10.3.3.4 *Results in persistent or significant disability or incapacity.*

10.3.3.5 *Is an important medical event.*

Any event that does not meet the above criteria, but that in the judgment of the investigator jeopardizes the patient, may be considered for reporting as a serious adverse event. The event may require medical or surgical intervention to prevent one of the outcomes listed in the definition of “Serious Adverse Event”.

10.4 *Steps to Determine if an Adverse Event Requires Expedited Reporting*

Step 1: Identify the type of AE using the NCI CTCAE v4.03.

Step 2: Grade the AE using CTCAE v4.03.

Step 3: Determine whether the AE is related to radiation therapy.

Attribution categories are as follows:

- Definite: The AE is *clearly related* to the radiation treatment.
- Probable: The AE is *likely related* to the radiation treatment.
- Possible: The AE *may be related* to the radiation treatment.
- Unrelated: The AE is *clearly NOT related* to the radiation treatment.

Step 4: Determine the prior experience of the AE.

Expected events are those that have been previously identified as resulting from administration of a similar radiotherapy treatment delivery. An AE is

considered unexpected, for expedited reporting purposes only, when either the type of event or the severity of the event is not listed in:

- The current known AE's listed in this protocol.
- The consent form.
- The current Investigator's Brochure

10.5 *Exceptions to AE and SAE Definitions*

For the purposes of this study, neither the condition, prolonged hospitalization, nor surgery are reported as AEs or SAEs under the following circumstances:

- Hospitalization or prolonged hospitalization is for a diagnostic or elective surgical procedure for a preexisting condition. Surgery should not be reported as an outcome of an AE if the purpose of surgery is elective or diagnostic and the outcome is uneventful.
- Hospitalization or prolonged hospitalization is due to social reasons (e.g. awaiting transport home)

10.6 *Reporting Requirements for Adverse Events*

10.6.1 Expedited Reporting

- The Principal Investigator must be notified within 24 hours of learning of any serious adverse events, regardless of attribution, occurring during the study or within 30 days of the administration of radiation therapy.
- The institutional officials must be notified within 10 business days of "any unanticipated problems involving risk to subjects or others" (UPR/UPIRSO).

The following events meet the definition of UPR:

1. Any serious event (injuries, side effects, deaths or other problems), which in the opinion of the Principal Investigator was unanticipated, involved risk to subjects or others, and was possibly related to the research procedures.
2. Any serious accidental or unintentional change to the Institutional Review Board (IRB) approved protocol that alters the level of risk.
3. Any deviation from the protocol taken without prior IRB review to eliminate apparent immediate hazard to a research subject.
4. Any new information (e.g., publication, safety monitoring report updated sponsor safety report), interim result or other finding that

indicates an unexpected change to the risk/benefit ratio for the research.

5. Any breach in confidentiality that may involve risk to the subject or others
6. Any complaint of a subject that indicates an unanticipated risk that cannot be resolved by the Principal Investigator.

10.6.2 Routine Reporting

All other adverse events such as those that are expected, or are unlikely or definitely not related to the study participation are to be reported annually as part of routine data submission.

10.7 *Stopping Rules*

Grade 3 or 4 toxicities will be evaluated by the primary investigator, and if radiation therapy is thought to contribute to the toxicity, the institutional officials will review it in detail. The nature of the toxicity will undergo a thorough review and determine if the study should be stopped for fear of excessive risk to future patients. Grade 5 toxicities (death) will be evaluated by the primary investigator and the institutional officials for review. If radiotherapy is felt to directly contribute to death then the institutional officials will determine if the study should be stopped.

11.0 DATA COLLECTION

11.1 *Online Database*

Data collection will utilize the REDCap database. REDCap is a secure web-based application designed for building and collecting data sets.

12.0 STATISTICAL CONSIDERATIONS

12.1 *Study Design/Study Endpoints*

The primary outcome will be any radiotherapy-related acute or chronic grade 3-5 toxicity as defined previously in the document. The study is designed as a two stage Phase II study as described below.

12.2 *Sample Size and Accrual*

Primary Aim

In this single-arm oncology trial evaluating the safety and efficacy of HDR brachytherapy for recurrent prostate cancer, one goal is to determine the toxicity

of single fraction focal treatment. Simon's two-stage²³ design is used to power this aim. The primary hypothesis is that the acceptable toxic response rate is less than or equal to 10.0% (p_1). The unacceptable toxic rate is set at 33% (p_0).

More concisely:

$$H_0: p_0 \geq .33$$

$$H_A: p_1 \leq .10$$

The null hypothesis is that the unacceptable toxic response rate is at least 33%. This will be tested against a one-sided alternative that the toxicity rate is 10% or less.

In the first stage, 7 patients will be accrued. If there are 2 or more toxic responses (radiation-related acute grade ≥ 3 GU or GI toxicity) in these 7 patients, the study will be stopped for safety reasons. Otherwise, 17 additional patients will be accrued for a total of 24 patients. Note that, under these conditions, the probability of stopping early is 73% if the toxic response rate is truly higher than 10.0%.

At the end of the second stage, the null hypothesis that the toxicity rate is 33% or higher will be rejected if more than 19 (non-toxic) responses are observed in 24 patients. When the true toxicity rate is 10.0%, this design yields a type I error rate of .046 and power of 81%.

Secondary Aim

We also will describe the freedom from biochemical recurrence, relapse-free survival, local control, elsewhere-prostate control, freedom-from local failure, freedom from distant metastasis, freedom from hormonal therapy, disease-free survival, cause-specific survival, and overall survival.

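### After patient 7 the plan has no numerical stopping boundary, although a 5th primary-endpoint toxicity already makes it impossible to reject the unacceptable rate

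*Combined protocol and SAP*

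**What the plan says.** Section 12.2 describes a Simon two-stage design. For stage 1 it says "In the first stage, 7 patients will be accrued"; with 2 or more toxic responses "in these 7 patients, the study will be stopped for safety reasons". With 0 or 1, "Otherwise, 17 additional patients will be accrued for a total of 24 patients". At the end of stage 2 the null hypothesis is "rejected if more than 19 (non-toxic) responses are observed in 24 patients". The Study Summary repeats these rules.

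Section 10.7 (Stopping Rules) has grade 3 or 4 toxicities assessed by the investigator and, where radiation is thought to contribute, by institutional officials. The toxicity "will undergo a thorough review and determine if the study should be stopped". Deaths are reviewed in a similar way. The section gives no count or rate, and mentions neither the 2-of-7 rule nor the final limit.

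Section 10.1 places the trial under the cancer center's Data Safety Monitoring Plan, whose content is not in the documents.

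**The concern.** More than 19 non-toxic outcomes in 24 means at most 4 toxicities. After a 5th, no later result can lead to rejection, yet the default in 12.2 is to go on to 24. As written, 1 toxicity in stage 1 followed by 17 in stage 2 (18 in all) would cross no numerical boundary.

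The primary endpoint is safety and the patients are being re-irradiated; Section 1.4 itself names re-irradiation in areas of overlap as the main limitation of the approach. Patients enrolled after the 5th event would take that risk without being able to change the primary test.

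**Working it through.** **Inputs.** From Section 12.2: 7 patients in stage 1, continue with 0 or 1 toxicity; 17 more to a total of 24; reject with at least 20 non-toxic, so at most 24 − 20 = 4 toxic; unacceptable rate 0.33, acceptable rate 0.10, one-sided. From Section 2.3.1: a 3-month endpoint.

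**1. Reproduce the stated figures.** With X ~ Bin(7, p) and Y ~ Bin(17, p), P(reject) = P(X=0)·P(Y≤4) + P(X=1)·P(Y≤3).

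- p = 0.33: 0.0606 × 0.2913 + 0.2090 × 0.1366 = 0.0462 (stated .046).
- p = 0.10: 0.4783 × 0.9779 + 0.3720 × 0.9174 = 0.809 (stated 81%).
- Stopping at stage 1: 1 − 0.0606 − 0.2090 = 0.730 at p = 0.33. This is the plan's 73%, although 12.2 attaches it to any rate above 10%; at 10% it is 0.150.

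**2. Earliest trigger.** One toxicity in the first 7, then patients 8 to 11 all toxic: the 5th event falls at patient 11, with 13 still to enrol.

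**3. When the 5th event occurs.** Let K be the patient number of the 5th toxicity. For K = 7 + j,

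P(continue and K = 7 + j) = Σ over x = 0, 1 of P(X=x) · C(j−1, 4−x) · p^(5−x) · (1−p)^(j−5+x), for j from 5−x to 17.

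Patients spared are 24 − K, with outcomes known at once.

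| True rate | Pass stage 1 | 5th event by patient 24 (of continuing) | Before patient 24 (of continuing) | Before patient 24 (of all trials) | Spared per continuing trial | Spared per trial overall |
|---|---|---|---|---|---|---|
| 10% | 85% | 4.9% | 3.9% | 3.4% | 0.15 | 0.13 |
| 20% | 58% | 37.5% | 33% | 19% | 1.6 | 0.9 |
| 33% | 27% | 82.9% | 79% | 21% | 5.0 | 1.3 |
| 40% | 16% | 94.0% | 92% | 15% | 6.8 | 1.1 |

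Expected sample size at 33% is 7 × 0.7304 + 24 × 0.2696 = 11.6 as planned, and 11.6 − 1.3 = about 10.2 with the rule.

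**4. Error rates with the rule.** Rejection means passing stage 1 and never reaching a 5th event. At 33%: 0.2696 − 0.2234 = 0.0462. At 10%: 0.8503 − 0.0413 = 0.809. Both are unchanged.

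**5. Delay.** The documents give no accrual rate, so suppose L further patients enrol before the 5th event is confirmed. The saving per continuing trial is Σ P(K=k)·max(0, 24 − k − L) / P(continue). At 33% this is 5.0 for L = 0, 4.2 for L = 1, 2.8 for L = 3 and 1.6 for L = 5.

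**6. Effect on the estimate.** A trial halted at patient K < 24 shows a naive rate of 5/K, anywhere from 5/11 = 45% to 5/23 = 22%. Averaged over halted trials, E[5/K | K<24] is 25%, 27% and 29% at true rates of 10%, 20% and 33%. Had the same trials run to 24, E[(5 + (24−K)p)/24 | K<24] would be 22%, 25% and 30%. So halting adds upward bias when the true rate is low. At 33% it adds almost none, and the naive rate lies below the truth because passing stage 1 selects trials with few early events.

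**The case against.** A reader might infer that nothing can stop the trial after stage 1, so that it must run to 24. The documents do not support that. Section 10.7 requires review of every grade 3 or 4 toxicity to which radiation is thought to contribute, with the possibility of stopping, so five qualifying events of those grades would mean five reviews. Sections 8.4.7 and 13.5 refer to a data monitoring committee, and the institutional plan in 10.1 may hold further rules. What is missing from the text at hand is a numerical trigger tied to the final test.

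A reader might also infer that the design is miscalculated, or that a 5th event shows an unacceptable rate. Neither follows. A Simon design without stage 2 curtailment is used here as defined, and its error rates reproduce. Five events in 24 is 21%, and failing to reject 33% does not prove a rate of 33%. At a true rate of 20% the rule would halt a third of continuing trials, although those trials could not have rejected the null in any case.

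The large percentages are conditional on passing stage 1, which already stops 73% of trials at 33%. The Study Summary states the primary aim as estimating the toxicity rate, and later patients do inform that estimate. These points limit the size of the gain; they do not supply the missing boundary.

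**Conclusion.** The point holds as a gap in monitoring. After patient 7 the documents set no numerical boundary, accrual to 24 is the default, and the discretionary review in 10.7 is not linked to the limit of 4 toxicities in 24. At a true rate of 33% the gain is modest across all trials and material within the trials that pass stage 1; it shrinks as confirmation is delayed. At a true rate of 10% the rule would rarely interfere.

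This rests on independent outcomes with a common toxicity rate, an assumed range for the confirmation delay, and a running count that uses the same events as the final test. The last condition is not yet met: 12.1 counts acute or chronic grade 3–5 toxicity, 12.2 counts acute grade 3 or higher GU or GI toxicity, and 2.3.1 sets a 3-month GU and GI endpoint. If the running count took in late events that the final test leaves out, a 5th event would no longer fix the decision and power could be lost.

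**What to change.** First reconcile the event definition across 12.1, 12.2 and 2.3.1. Then add to 12.2, and cross-reference in 10.7 beside the 2-of-7 rule:

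*Accrual is suspended when the 5th toxicity meeting the primary-endpoint definition used in the final test is confirmed among enrolled patients, because the null hypothesis can no longer be rejected.*

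State as well that the reported toxicity rate and its interval will allow for both stopping rules. If the institutional monitoring plan already holds an equivalent boundary, citing it in 10.7 would be enough.

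The cost is a sentence or two of text, nothing in type I error or power, and, only in trials that can no longer reject the null, fewer patients for the secondary endpoints and a less precise toxicity estimate.

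### The 73% chance of early stopping is claimed for any toxicity rate above 10% but is reached only at 33%, and the type I error is tied to the wrong true rate

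*Combined protocol and SAP*

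**What the plan says.** Section 12.2 (Sample Size and Accrual) uses a Simon two-stage design with an unacceptable toxicity rate of 33% (p0) and an acceptable rate of 10% or lower (p1). The first 7 patients are assessed, and 2 or more toxicities stop the trial. Otherwise 17 more are accrued, for a total of 24, and the null hypothesis of a rate of 33% or higher is rejected if more than 19 patients are free of toxicity, that is, with 4 or fewer toxicities.

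Three statements about this design are at issue:

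- Early stopping: "the probability of stopping early is 73% if the toxic response rate is truly higher than 10.0" per cent.
- Error rates: "When the true toxicity rate is 10.0%, this design yields a type I error rate of .046 and power of 81" per cent. The Study Summary (Statistical Methodology) repeats this sentence.
- Alternative hypothesis: "This will be tested against a one-sided alternative that the toxicity rate is 10% or less".

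No operating characteristic is attached to a true rate of 33%, and none is given for rates between 10% and 33%.

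**The concern.** The chance of seeing 2 or more toxicities in 7 patients rises continuously with the true rate, so one figure cannot describe every rate above 10%. A stopping probability quoted for a Simon design is normally the one under the null, here 33%. The text appears to have put 10% where 33% was meant, in both the stopping sentence and the error sentence. A type I error at a true rate of 10% is a contradiction, because the null is false there.

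Toxicity is the primary endpoint, and section 1.5 says that data on the safety of this combination are limited. The 2-of-7 rule is the only stopping rule with a number attached, and 73% is the only early-stopping probability given. Taken at face value, it says that a regimen with toxicity above the acceptable rate would be halted after 7 patients about three times in four. An ethics board or monitoring body relying on it would think the trial better protected against intermediate toxicity rates than it is.

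**Working it through.** **Inputs, all from section 12.2.** Stage 1: n1 = 7, stop at 2 or more toxicities. Total n = 24 (7 + 17). Reject the null at 4 or fewer toxicities. p0 = 0.33, p1 = 0.10.

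**Formulas**, with t the true toxicity rate:

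- P(stop early) = 1 − (1−t)^7 − 7t(1−t)^6
- P(reject H0) = P(Bin(7,t)=0) × P(Bin(17,t)≤4) + P(Bin(7,t)=1) × P(Bin(17,t)≤3)

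**Step 1: reproduce the plan's three figures.**

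- Early stopping at t = 0.33: 1 − 0.0606 − 0.2090 = 0.730. This is the plan's 73%.
- Rejection at t = 0.33: 0.0606 × 0.2913 + 0.2090 × 0.1366 = 0.0462. This is the plan's .046.
- Rejection at t = 0.10: 0.4783 × 0.9779 + 0.3720 × 0.9174 = 0.809. This is the plan's 81%.

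A search for the optimal Simon design (non-toxicity rates 0.67 and 0.90, type I error at most .05, power at least .80) returns these same boundaries. Other readings do not match all three figures: p0 = 1/3 gives early stopping of .737 and a type I error of .043, and ignoring stage 1 gives .063 and power of .915. So the numbers are right for the design, and 73% and .046 both belong to a true rate of 33%.

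**Step 2: evaluate the rule at the rates the sentence covers.**

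| True toxicity rate | P(stop after 7) | Overstatement by 73%, points | P(reject H0) |
|---|---|---|---|
| 10% | 0.150 | 58 | 0.809 |
| 11% | 0.175 | 56 | 0.769 |
| 15% | 0.283 | 45 | 0.588 |
| 20% | 0.423 | 31 | 0.360 |
| 25% | 0.555 | 17 | 0.187 |
| 30% | 0.671 | 6 | 0.082 |
| 33% | 0.730 | 0 | 0.046 |
| 35% | 0.766 | none | 0.031 |
| 40% | 0.841 | none | 0.010 |

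Early stopping reaches one half at a true rate of about 23%. At 20%, twice the acceptable rate, the trial goes on to 24 patients with probability 1 − 0.423 = 0.577.

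**Step 3: the error sentence.** At 10% the only rejection probability is 0.809, the power. A type I error exists only where the null holds, at 33% or above, and is largest at 33%.

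**Step 4: the alternative.** Rejection is allowed with up to 4 of 24 toxicities, an observed rate of 16.7%. It happens 59% of the time at a true rate of 15% and 36% of the time at 20%. Rejection therefore supports a rate below 33%, not a rate of 10% or less.

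**The case against.** The strongest reply is that nothing in the design is wrong. All three figures come from one coherent design, and p0, p1 and the boundary stand beside them, so a statistician can spot the slip and correct it. This is true, and it limits the remedy to wording. It does not make the stopping sentence correct, and no correct figure is given elsewhere.

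Other points stand in part:

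- 73% is a floor for all rates of 33% or more, so the overstatement is confined to rates between 10% and 33%. The 58-point gap is the extreme, at the edge of the rate the plan accepts.
- The .046 sentence can be read correctly by anyone who knows that a type I error is defined under the null, which the preceding sentence gives. It is a mislabelled condition and does not itself alter protection; the overstatement comes from the 73% sentence.
- The Study Summary and section 12.3 describe the test as asking whether toxicity is lower than the hypothesized rate, and nowhere does the plan promise to report rejection as proof of 10% or less. The restated alternative would bring section 12.2 into line with those descriptions.
- The rejection probabilities at 15% and 20% contradict no statement in the plan. They are properties of the gap between 10% and 33% and are used here only to show what rejection can support.
- Section 10.7 provides for review of individual grade 3 to 5 events, with the option to stop the trial, so safety does not rest on the 2-of-7 rule alone. That review has no numerical threshold and so supplies no stopping probability.

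**Conclusion.** The concern holds. The early-stopping statement is false for every true rate between 10% and 33%: the correct probability runs from 15.0% just above 10%, through 42.3% at 20%, to 73.0% at 33%. The type I error of .046 is correct at 33% and is wrongly attached to 10% in both section 12.2 and the Study Summary. The wording of the alternative claims more than rejection can show. The sample size, boundaries, type I error and power all stand.

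The calculation assumes only independent patients with a common toxicity rate and the decision rule applied exactly as written. Because the misstatement concerns the only quantified safety stop for the primary endpoint, it should be corrected and not left for readers to work out.

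**What to change.** Three changes of wording:

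1. **Section 12.2, early stopping.** Say that the probability of stopping after stage 1 is 73% if the true toxicity rate is 33%, 42% if it is 20%, and 15% if it is 10%.
2. **Section 12.2 and the Study Summary, error rates.** Say that the type I error is .046 at a true rate of 33% and the power is 81% at a true rate of 10%.
3. **Section 12.2, alternative.** State H_A as p < 0.33, with power evaluated at p = 0.10, and add that rejecting the null supports a toxicity rate below 33%, not one of 10% or less.

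The design, boundaries and sample size do not change, and no patients or time are added. The only cost is that the stated early-stopping protection becomes less favourable.
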